**- Magnetic resonance spectroscopy (MRS)**

MRS is used to quantify the hepatic and cardiac fat content and ATP/AMP ratio. A fat content of more than 50 mg/g corresponding 5 % of the wet weight is diagnostic for hepatic steatosis,

measured by MRS as FF % > 5,6 (23). MRS is used to distribute the participants into group 1 and group 2.

### **- Fibroscan**

Fibroscan is used to assess if NAFL is progressing into NASH. Values < 1 kPa is a sign of absence of NASH. Values > 8 kPa is a strong predictor for NASH with fibrosis. Fibroscan is based on ultrasound technology and is a non-invasive examination.

### **Visit 1**

The purpose of visit 1 is to take blood samples to isolate and label VLDL-TG and to screen for genetic susceptibility (64). Furthermore we wish to determine body composition by performing DXA (dual-energy X-ray absorptiometry) scan and determine the cardiac contractility and pump function via echocardiography and finally to advise the participant concerning physical activity and diet up to the study day.

### **- Blood tests**

- VLDL-TG will be labelled with 20  $\mu\text{Ci}$  [ $1\text{-}^{14}\text{C}$ ]triolein and isolated via centrifugation. Labelled VLDL particles were tested for bacterial growth to ensure sterility and stored at 5 °C for reinfusion on the study day.

### **- DXA-scan**

- Is performed to assess total body fat and lean body mass.

### **- Echocardiography ("Echo")**

Is a non-invasive test that uses high frequency sound waves (ultrasound) to make pictures of the heart, and it can give information about the size and shape of the heart and about the function of the heart valves and pumping performance. In atherosclerosis, where the blood supply to the heart muscle is reduced, the echocardiography can show reduced muscle strength in parts of the heart, where the blood supply is reduced.

Echocardiography will be performed by a chief physician from the Department of Cardiology, AUH.

### - Interview by a dietician

The participants will be interviewed by a dietician regarding physical activity and diet up to the study day. The volunteers were requested to avoid vigorous exercise and were provided a isocaloric (weight maintaining) diet (55 % carbohydrate, 15 % protein, and 30 % fat) delivered from the Clinical Trial Unit, AUH, for the 3 days preceding the study day.

### The Study Day (Visit 2)

The participant will be admitted to the Clinical Trial Unit, CTU, at 22.00 the evening before the study. The participants are only allowed to ingest tap water after the admission to CTU.

The study can be divided into a 3 hours basal period (0-180 min) and a 5 hours clamp period (180-450 min). A hyperinsulinemic euglycaemic clamp is used to determine insulin sensitivity. During insulin clamp, hyperinsulinemia, is achieved by infusing constant intravenous insulin of 0,6 mU/kg/min (Actrapid, Novo Nordisk) and euglycemia is maintained via concomitant intravenous 20 % isotonic glucose infusion, so the plasma glucose is constantly at 5 mM. Plasma glucose levels are monitored via frequent intervals during the study.

### Flow sheet over the study day

Time	06.30	07.00	7.30	8.00	8.30	9.00	9.30	10.00	10.30	11.00	11.30	12.00	12.30	13.00	13.30	14.00	
Minutes	-30	0	30	60	90	120	150	180	210	240	270	300	330	360	390	420	
Period		Basal						Clamp (insulin+glucose infusion)									
Infusions																	
Glucose								Isotonic 20 %									
Actrapid								0,6 mU/kg/min									
TRACERS																	
 C-VLDL			14C-VLDL-TG infusion, 20 % bolus initially, 80 % constant infusion														
 C-palmitate																	
9,10-  H-palmitate																	
BLOOD SAMPLES																	
 C-VLDL		x						xxxx								xxxx	
9,10-  H-palmitate							x	xxxx				x				xxxx	
Plasma glucose	x	x	x	x	x	x	x	x	x	x	x	x	x	x	x	x	
FFA		x		x		x		x		x	x	x		x		x	
Insulin		x		x		x		x		x		x		x		x	
Plasma lipid		x		x		x		x		x		x		x		x	
Plasma Li-hep		x		x		x		x		x		x		x		x	
Plasma EDTA		x		x		x		x		x		x		x		x	
Serum		x		x		x		x		x		x		x		x	
EXAMINATIONS																	
Insertion of catheter	x																
PET/CT																	
Muscle biopsy		x															
Adipose tissue biopsy		x															
Calorimetry				x									x				
Breath sample		x						xxxx									
Urin sample								x								x	

At  $t = -30$ , catheters were placed in an antecubital vein and a contralateral heated hand vein in order to obtain arterialized blood. If it is difficult to extract blood from a hand vein in rare occasions, an artery cannula can be inserted with help from a nurse or a doctor from the Department of Anaesthesiology, AUH.

At  $t=0$ , a primed-constant intravenous infusion of  $[1-^{14}\text{C}]$ triolein-labelled VLDL-TG (priming with bolus of 20 % of labelled VLDL, 80 % is given as continuous infusion) was initiated to determine VLDL-TG kinetics. Blood samples are obtained to measure VLDL-TG secretion rate.

At  $t=0$  and at  $t=360$ , muscle and adipose tissue biopsies are obtained under sterile conditions. The samples will be quick-frozen for subsequent analysis.

At  $t=60$  and  $t=240$  an intravenous bolus injection of IV  $^{11}\text{C}$ -palmitate will be administered and PET/CT scans and blood samples will be obtained after 50 minutes. Blood samples are obtained to determine uptake, oxidation and re-esterification of FFA in heart and in liver.

At  $t=180$  the insulin clamp period is initiated with IV insulin infusion and IV glucose infusion.

FFA turnover is examined via a constant infusion of  $[9,10-^3\text{H}]$  palmitate (1 hour) in basal and clamp periods. Blood samples to determine palmitate turnover, lipogenesis, and specific activity in blood and FA derivatives will be obtained in the beginning of the  $[9,10-^3\text{H}]$ -palmitate infusion and after 30, 40, 50 and 60 minutes of infusion.

Breath samples will be obtained during the study to examine the  $^{14}\text{CO}_2$  specific activity to determine VLDL-TG FA oxidation.

Indirect calorimetry will be done to examine the energy metabolism and substrate oxidation rate.

Blood samples are taken at different intervals to determine glucose, FFA, insulin and tracer concentrations.

After blood sampling at  $t=450$  the catheters will be removed and the participants will be offered a meal.

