### *NAFLD and risk of cardiovascular disease*

Mediators linking NAFLD with myocardial dysfunction are not known but are presumed to include both pre-hepatic (e.g. ectopic/cardiac fat) and hepatic mechanisms with potential direct

impact on cardiac function and mirrored at the whole body level by metabolic inflexibility. Metabolic inflexibility is the inability to shift efficiently between glucose and lipid oxidation due to a chronic increase in plasma FFA caused by insulin resistant anti-lipolysis and hepatic VLDL-TG hypersecretion (13).

The metabolic dysfunction of the myocardium in NAFLD and T2DM includes 1) reduced basal and insulin stimulated glucose oxidation, 2) reduced phosphate creatinine/adenosine triphosphate (PCr/ATP) ratio (a marker of the myocardial fuel utilization) and 3) a potential reduced FFA oxidation (9,19). Both intrahepatic TG and TG secreted into the bloodstream as lipoproteins (VLDL-TG) are derived from plasma FFA and released into the bloodstream via lipolysis in peripheral adipose tissue (21). Human studies suggest that the circulating FFA in combination with insulin resistance determine the amount of VLDL particles produced by the liver and, hence the quantity of TG released into the blood (22, 27). During basal fasting, the amount of visceral fat correlates directly to the delivery of liver FFA from the circulation (yet with significant difference between men and women) (2).

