#### *Insulin resistance and its role in the pathogenesis of NAFLD*

Immediately after a meal, insulin increases and, in healthy people, reduces blood glucose (BG) and results in an almost immediate halt in VLDL secretion. The effect of insulin is, however, severely impaired in NAFL, NASH and type 2 diabetic patients both in the liver (23,28), adipose tissue (24-26), and skeletal muscle (27). The overall effect is an increased amount of VLDL-TG in the blood with subsequent risk of atherosclerosis and ectopic fat accumulation in e.g. the myocardium (10). Although the effect of reduced insulin sensitivity on increased FFA and VLDL-TG levels are well-documented (28), it is uncertain to what extent each factor contributes quantitatively to NAFLD due to the liver's anatomical localization and the lack of robust tracer methods to assess VLDL-TG production rate. Even though NAFLD is recognized as a strong predictor of CVD risk factors associated with MS (5), this is, however, not always the case, and has led researchers to question whether NAFLD is the result of insulin resistance or whether insulin resistance is secondary to NAFLD, or both (29). Studies have shown that the degree of NAFLD in obese, insulin resistant subjects correlates with cellular and intracellular insulin resistant manifestations in many metabolic processes. This is the case in both liver, muscle, and adipose tissue, such as FFA uptake in liver and muscle, hepatic de novo lipogenesis, altered lipogenic enzyme activity in liver and adipose tissue, muscle, mitochondrial/TCA cycle activity, and cardiac steatosis with impaired ventricular function (10, 31, 32). The multiple direct and sometimes temporary relationships between NAFLD and the

heart and peripheral tissues indicate that insulin resistance and metabolic inflexibility is a key component of NAFLD, but also that significant integrated pathophysiological cross-talk exists between the heart, liver, skeletal muscle and adipose tissue. Thus, insulin resistance in combination with hyperinsulinemia and increased hepatic FFA delivery may promote liver fat accumulation by increasing hepatic TG production and de-novo lipogenesis (12, 21, 24, 33). In addition, the development of NAFLD is also assumed to be an imbalance between hepatic FA delivery (FA uptake and/or de-novo synthesis) and hepatic lipid export (i.e hepatic FA oxidation and/or VLDL-TG secretion) as previously described.

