### **$^{11}\text{C}$ -palmitate:**

A total dose of 400 MBq will be administered to participants while scanning the heart and liver. Metabolite correction ( $^{11}\text{CO}_2$  and  $^{11}\text{C}$ -TG) will be performed using our own validated population mean (36,37). In-put function is obtained from images covering the lumen of the left ventricle. FFA turnover in liver and heart is determined using  $^{11}\text{C}$  palmitate PET technique.

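### Does the blood-sample timing around the PET scans leave the plasma FFA value behind the primary cardiac endpoint in doubt?

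*Combined protocol and SAP*

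**What the plan says.** Flow sheet over the study day gives the tracer as a bolus at t=60 in the basal period and at t=240 in the clamp period, and adds that "PET/CT scans and blood samples will be obtained after 50 minutes". It gives the purpose of the blood: "Blood samples are obtained to determine uptake, oxidation and re-esterification of FFA in heart and in liver". The start of insulin is described under the same heading, where "the insulin clamp period is initiated with IV insulin infusion and IV glucose infusion" (timed at 180 minutes). Later text there is general: "Blood samples are taken at different intervals to determine glucose, FFA, insulin and tracer concentrations".

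The section on 11C-palmitate says the dose "will be administered to participants while scanning the heart and liver", and that "In-put function is obtained from images covering the lumen of the left ventricle". It takes the metabolite correction from a population mean validated by the group itself. Primary Endpoint names cardiac FFA uptake and oxidation by this PET method. The section FFA turnover describes a plasma palmitate assay, but only for the tritiated tracer. No section gives a formula that combines a plasma FFA concentration with the PET result.

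**The concern.** The blood drawn with the PET is said to serve the quantities in the primary endpoint, yet the stated timing and the sampling schedule do not appear to meet. If the cardiac estimate is a molar rate, a plasma concentration presumably multiplies the PET result, and the analyst could take it from any of several samples.

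The clamp scan makes this look more serious, because it begins 60 minutes after insulin starts and plasma FFA may still be falling. The background sections refer to "a chronic increase in plasma FFA caused by insulin resistant anti-lipolysis and hepatic VLDL-TG hypersecretion" and state that "the degree of NAFLD in obese, insulin resistant subjects correlates with cellular and intracellular insulin resistant manifestations in many metabolic processes". If FFA falls by different amounts in the two groups, the choice of sample would change the clamp comparison, with only 10 participants per group.

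**Working it through.** The plan has no figure on this point to reproduce. The check sets the times side by side and then tests how much the choice could matter.

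**Times**
- Literal sampling times: 60 + 50 = 110 and 240 + 50 = 290.
- FFA row of the flow sheet: 0, 60, 120, 180, 240, 270, 300, 360, 420. Neither 110 nor 290 is there.
- Columns of the flow sheet: every 30 minutes from -30 to 420. Neither time could appear for any analyte.
- The sheet does not try to show exact times. The text has tritiated palmitate sampled 30, 40, 50 and 60 minutes into each infusion. The sheet shows these four samples as a cluster in a single cell, although they span half an hour.
- Nearest later FFA marks: 120 - 110 = 10 minutes and 300 - 290 = 10 minutes.

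**Which reading of the 50 minutes works**

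The tracer section has injection during scanning and an input function taken from left-ventricular images. An image-derived input function needs images from the bolus onward, so a scan that started 50 minutes later would not supply it. The workable reading is a window from the bolus: 60 to 110 and 240 to 290. On that reading, 110 and 290 are ends of windows, not sampling times. FFA marks within or at the start of the windows are t=60 (basal) and t=240 and 270 (clamp), with t=120 and t=300 just after. FFA is the only otherwise hourly analyte with an extra mark at t=270, inside the clamp window.

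**Is a molar cardiac rate planned?**

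Statistical analysis gives 20% as 12.5 µmol/min, in a sentence that covers both palmitate oxidation and VLDL-TG secretion. The stated VLDL-TG mean is 60 µmol/min, and 0.20 × 60 = 12, close to 12.5. No cardiac palmitate mean is given. The unit therefore fits VLDL-TG secretion at least as well and is weak evidence about the scale of the PET endpoint.

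**Sensitivity, on assumptions only**

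Assume the estimate is proportional to plasma FFA and that FFA falls linearly from t=240 to t=300 by x. The value relative to t=240 is 1 - x/2 at t=270 and 1 - x at t=300. The table shows how much the NAFLD to non-NAFLD ratio changes relative to using t=240.

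| Assumed fall, NAFLD / non-NAFLD | t=270 | t=300 (outside window) |
|---|---|---|
| 20% / 20% | 0.90/0.90 = 1, no change | 0.80/0.80 = 1, no change |
| 20% / 30% | 0.90/0.85 = 1.059, +5.9% | 0.80/0.70 = 1.143, +14.3% |
| 10% / 30% | 0.95/0.85 = 1.118, +11.8% | 0.90/0.70 = 1.286, +28.6% |

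The mean over 240 to 290 sits at t=265, where the value is 1 - x × 25/60: 0.9583, 0.9167 and 0.8750 for x = 10%, 20% and 30%. Against that mean, the t=270 sample differs by (0.90/0.85)/(0.9167/0.8750) = 1.011 and (0.95/0.85)/(0.9583/0.8750) = 1.020, that is +1.1% and +2.0%. The larger figures arise only when a sample from the start of the window is set against one taken after its end.

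**The case for a change.** The strongest case for acting is that a computation inside the primary endpoint is not written down. Neither the input function nor the metabolite correction uses the participant's own blood, so the role of the blood drawn with the PET is unexplained, and a plasma FFA multiplier is a natural guess. The 14C and tritiated tracers each have a labelled row among the blood samples; 11C has none. Several candidate samples exist, and a couple of sentences would settle the matter at no cost.

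Part of this stands: no section says whether plasma FFA enters the cardiac estimate, or which sample would supply it. The rest is weaker. The sentence on PET blood names no analyte, and tracer concentrations are among the things the plan measures in blood. The 11C and PET/CT rows of the flow sheet are blank in the extracted text, so timing drawn there may have been lost. The sample-size text refers to the group's own earlier studies with this tracer, so a method exists, although its details cannot be seen here. Nothing documents that the choice would be made after the data are known. A differential fall in FFA is also extrapolated: the background statement concerns obese, insulin-resistant subjects in general, whereas the trial compares two groups with type 2 diabetes matched for age and BMI.

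**Conclusion.** No change to the plan is needed. The apparent timing conflict comes from reading a coarse 30-minute grid as exact and a loosely worded sentence as a sampling time; the tracer section resolves the scan wording, which is a clerical matter. What remains is missing detail about a laboratory calculation. FFA is already measured around both scans, so whichever sensible rule the group's method uses can be applied to both groups with the scheduled samples. An interpolated window mean would be one acceptable rule among several, and it would replace no stated method.

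No bias or magnitude can be drawn from the documents. The 5.9% and 11.8% within the clamp window depend on assumed unequal falls in FFA and on an estimate proportional to plasma FFA. With equal falls, or with an endpoint expressed as a rate constant, the effect is zero. This conclusion rests on reading the 50 minutes as a scan window from the bolus and on the FFA row having been extracted in alignment, which the fully filled glucose row supports.

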## **Procedures**

### **Biopsies**

Muscle biopsies are taken under local anaesthesia with 6 ml 10 mg/ml lidocaine under sterile conditions from the vastus lateral muscle (approx. 0.2 g). Adipose tissue biopsies are taken from the subcutaneous adipose tissue of the abdomen and femur by a modified liposuction technique with a 2.1 mm cannula, also under local anaesthesia.

### **PET / CT scans**

PET scans is a minimal invasive nuclear medicine examination, often used to diagnose cancers, but can also be used to diagnose cardiovascular diseases. . A modern PET/CT scan can make images of the whole body within 10-20 minutes (56,57). Scans are performed using an integrated Siemens Biograph 64 PET / CT with 21 centimetres of field of view which covers the heart and liver. In connection with all PET scans, a simultaneous low-dose CT scan is performed to co-locate the PET-positive areas as well as to correct for tissue attenuation. The  $^{11}\text{C}$  palmitate tracer will be given as an IV bolus injection through a catheter into an elbow vein.

### **$^{11}\text{C}$ -palmitate:**

A total dose of 400 MBq will be administered to participants while scanning the heart and liver. Metabolite correction ( $^{11}\text{CO}_2$  and  $^{11}\text{C}$ -TG) will be performed using our own validated population mean (36,37). In-put function is obtained from images covering the lumen of the left ventricle. FFA turnover in liver and heart is determined using  $^{11}\text{C}$  palmitate PET technique.

### **Echocardiography**

The ability of the heart to contract and fill is measured by echocardiography.

### **VLDL-triglyceride turnover**

Turnover is determined by isotope dilution technique with continuous infusion of ex-vivo labelled VLDL triglyceride (23, 58). One week before the examination, a 60 ml venous blood sample is taken under sterile conditions. VLDL triglyceride will be labelled with 20  $\mu\text{Ci}$  [1-

C] triolein and subsequently isolated by ultracentrifugation (40,000 rpm for 18 hours at 4 ° C). Sterility will be ensured by culturing before the sample is used for re-infusion. The radiolabelled VLDL will be stored at 5 ° C until the day of the study. On the day of the examination, the patient's own [1-C] triolein labelled VLDL triglyceride will be infused and the sample now contains only about 10% of the initial triolein dose used, due to decay during the week. Blood samples will be taken on the day of the study as indicated to determine VLDL triglyceride concentration and substrate activity.

### **Oxidation of VLDL-TG**

Determined by measuring CO2 concentration and specific activity in the exhaled air (determined by hyamine) as previously described (41, 58).

### **VLDL-TG-FA uptake into muscle and adipose tissue**

Determined by measuring FFA concentration and specific activity in muscle biopsies and fat biopsies.

### **FFA turnover in the liver and heart**

Measured using PET technique after bolus administration of C palmitate and subsequently determining the fatty acid oxidation, re-esterification and secretion of the liver and heart.

### **Lipoprotein lipase activity**

Heparin-releasable lipoprotein (LPL) activity in adipose tissue is measured in fat biopsies after incubation in 5 U / ml heparin for 45 minutes at room temperature. The solution is then analysed for LPL activity using the “glycerol-stabilized substrate” method (59). For each tissue analysis, “post-heparin plasma” (PHP) is included as an internal standard to correct for substrate variation. Different dilutions of PHP are used to validate a linear response. Results are given as U / μmol FFA / hour / g.

### **FFA turnover**

Turnover is determined by isotope dilution technique with 2 times 1-hour continuous infusion of [9,10-H] palmitate (0.3 μCi / min total corresponding to 36 μCi) (60). Plasma FFA (palmitate) concentration and specific activity are determined by HPLC (high pressure liquid

chromatography) using [2H31] palmitate as internal standard. We have shown that our sample preparation does not cause in vitro hydrolysis of TG fatty acids or phospholipids. A quality control standard will be included with each assay to ensure minimal variation in the preparation of standard curves.

### **Resting energy expenditure (REE) and respiratory quotient (RQ)**

Determined by indirect calorimetry (Deltatrack Metabolic Monitor, Datex, Helsinki, Finland). From these measurements, net lipid and glucose oxidation can be calculated. Protein oxidation will be estimated from the excretion of urea in the urine (61).

### **Body composition**

Total body fat and fat-free mass are determined by DXA scan (Hologic QDR 2000).

## **Primary Endpoint**

- FFA uptake and oxidation as well as energy utilization in the heart ([11C] palmitate PET)

## **Secondary Endpoints**

- Pump function of the myocardium and left ventricular function (via echocardiography)
- FFA uptake, oxidation and re-esterification in the liver ([11C] palmitate - PET technique)
- VLDL-TG secretion ([1-14C] VLDL - isotope dilution technique)
- VLDL-TG oxidation (CO2 in exhaled air)
- VLDL-TG deposition in adipose tissue (fat biopsy ~ 1 g)
- Glucose metabolic tests and other blood tests. Intracellular signalling pathways in muscle and adipose tissue (AMPK, LKB1, ACC, CD36, ATGL, HSL, perilipine, G0S1, CGI58, GLUT4, and cytochrome C) as well as study for the genotypes of PNPLA3 and TM6SF2 in subjects with NAFLD.

### **Statistical analysis**

Sample sizes are based on estimates of cardiac palmitate from two recent studies in type 2 and nondiabetic men (28,29), as well as on prior experience regarding mean basal VLDL-TG secretion of 60  $\mu\text{mol}/\text{min}$  (SD of diff: 10  $\mu\text{mol}/\text{min}$ ). To detect a difference in palmitate oxidation as well as on VLDL-TG secretion between 2 experimental days of 20% (12.5 (SD 6.25)  $\mu\text{mol}/\text{min}$ ) with power 0.80 and  $\alpha$  5%, seven subjects are needed using two-sample t-test. Group comparisons will be done with standard statistical methods (ANOVA, t-test for parametrical data) and p-value under 0,05 will be assumed to be statistical significant. Corrections will be examined using Pearson's or Spearman's test. With 10 participants in each group, we would be able to determine a 30 % increased uptake of FFA in liver in subjects with NAFLD (power: 0.80). This is based on estimates of palmitate uptake in liver and FA oxidation in the heart from our previous studies, where we used the same  $^{11}\text{C}$ -palmitate tracer (37,50).

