## **Materials and Method**

### **Inclusion criteria**

- 20 study participants with T2DM (definition (49)) will be recruited:
- Group 1: 10 men/women with NAFL and/or NASH, confirmed fat fraction (FF) % > 5,6 assessed using MR spectroscopy (MRS)
- Group 2: 10 men/women matched for age and BMI without NAFLD (definition (47))
- Age of 30-70 years
- Non-smokers
- Written consent before the study start

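### VLDL-TG secretion: the endpoint scale is not stated, and the unadjusted comparison of age- and BMI-matched groups makes no use of the DXA fat-free mass already measured

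*Combined protocol and SAP*

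**What the plan says.** - **Scale.** The only figures for VLDL-TG secretion are in the sample-size text of Statistical analysis: "prior experience regarding mean basal VLDL-TG secretion of 60" µmol/min, and a target difference worded as "between 2 experimental days of 20% (12.5 (SD 6.25", also in µmol/min. The Secondary Endpoints list names secretion and the tracer method, but no unit and no body-size denominator.
- **Analysis.** "Group comparisons will be done with standard statistical methods (ANOVA, t-test for parametrical data" is all that is said about group comparisons. No covariate and no scaling are named.
- **Groups.** Under Inclusion criteria, group 2 is "10 men/women matched for age and BMI without NAFLD". Both sexes are eligible and no matching on sex is stated. Group membership follows from liver fat on MRS, so nothing is randomised.
- **Body composition.** "Total body fat and fat-free mass are determined by DXA scan". The scan belongs to Visit 1, before the study day. No section connects it to the VLDL-TG comparison.

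**The concern.** A whole-body secretion rate can be expected to depend partly on body size. BMI is the only size-related matching factor, and it does not fix size: at equal BMI, body mass varies with the square of height, and a man and a woman of the same BMI can differ in lean mass.

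Two things follow. First, any between-person variation that fat-free mass would explain stays in the error term, and with 10 per group precision is scarce. Second, because the groups are defined by disease status, body size or sex mix may differ between them for reasons other than chance. An unadjusted test would then attribute that difference to NAFLD, or let it hide a NAFLD effect.

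The unstated scale adds a smaller problem: µmol/min, per kg and per kg fat-free mass all remain open after the data are seen.

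**Working it through.** **1. The plan's own figure.** Inputs from Statistical analysis: difference 12.5, SD 6.25, "with power 0.80 and" alpha 5% (two-sided assumed, as sidedness is not stated), and "seven subjects are needed using two-sample t-test".
- Standardised difference: 12.5 / 6.25 = 2.0. A two-sample t-test (noncentral t) needs 6 per group. Power is 0.93 at 7 per group and 0.99 at the planned 10.
- With the other quoted spread, an SD of differences of 10, a paired t-test needs 8 and has power 0.79 at 7.
- Seven is therefore roughly reproduced, on the first route only if it means per group.
- 20% of 60 is 12.0, while 12.5 is 20% of 62.5. The difference is immaterial here.

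**2. What BMI matching leaves free.** At equal BMI, mean heights of 175 and 170 cm give (175/170)² − 1 = 6.0% more body mass.

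**3. Does chance imbalance give false positives?** No. Under randomly varying size, that variation is already in the t-test's standard error. A 10 v 10 simulation with the outcome proportional to height squared (assumed height SD 8 cm) plus noise, and no group effect, rejected in 5.1% of runs.

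**4. Precision.** Assume a within-group correlation r between secretion and fat-free mass. The residual SD is multiplied by √(1 − r²): 0.95 at r = 0.3, 0.87 at 0.5, 0.80 at 0.6. Estimating the slope multiplies the variance on average by 1 + 1/(20 − 4) = 17/16, and the error degrees of freedom fall from 18 to 17. Adjustment thus breaks even on variance when (1 − r²) × 17/16 = 1, that is r² = 1/17, r ≈ 0.24.

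Power at a standardised difference of 1.325, chosen because the unadjusted test there has power 0.80 (20,000 simulated trials per setting, 10 per group, two-sided 5%):

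| Assumed r | t-test | ANCOVA |
|---|---|---|
| 0 | 0.80 | 0.77 |
| 0.3 | 0.80 | 0.81 |
| 0.5 | 0.80 | 0.88 |
| 0.6 | 0.80 | 0.92 |

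At the plan's 12.5 / 6.25, the unadjusted test has power of about 0.99 and ANCOVA 0.98 to 1.00, so adjustment gains almost nothing if that SD is right for a between-person comparison.

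**5. A systematic difference.** Assume secretion proportional to fat-free mass, with a mean of 60.
- A true group difference in fat-free mass of 5% or 10% shifts secretion by 60 × 0.05 = 3.0 or 60 × 0.10 = 6.0 µmol/min. That is 25% or 50% of a 12 µmol/min difference.
- For sex mix, assume a male:female fat-free mass ratio ρ of 1.2 to 1.4. With m₁ and m₂ men per group, the shift is 60 × [(m₁ρ + 10 − m₁) / (m₂ρ + 10 − m₂) − 1].
  - 6 v 4 men: 60 × (11.2/10.8 − 1) = 2.2, up to 60 × (12.4/11.6 − 1) = 4.1 µmol/min.
  - 7 v 3 men: 60 × (11.4/10.6 − 1) = 4.5, up to 60 × (12.8/11.2 − 1) = 8.6 µmol/min.

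The sign depends on which group is larger or has more men. None of these inputs is in the documents, so the results show scale and do not predict a bias.

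**The case against.** **Chance imbalance is not a separate harm.** A reader might infer that an ordinary 5 cm gap in mean height could mimic part of the 20% target and so produce false positives. Step 3 shows otherwise: chance imbalance and noise are the same variance and must not be counted twice. This objection stands in full. Bias needs a systematic difference between the groups, and the documents give no evidence that one exists. They only leave it unguarded.

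**The plan does not commit to an unscaled analysis.** A reader might infer that it does. The µmol/min figure is a sample-size input, and the endpoint carries no unit, so reporting per kg fat-free mass is not excluded. This also stands: the defect is an unspecified scale and adjustment. Matching is on age as well as BMI.

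**The scope is narrow.** Systemic palmitate turnover is described under FFA turnover but is not a listed endpoint. VLDL-TG oxidation is derived from breath measurements and may be reported as a fraction, which need not grow with body size. The primary endpoint, cardiac PET, is not affected by this point.

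**The power gain is conditional.** It is calculated at an effect chosen to give 0.80. The plan's own inputs leave almost no room for gain, and the 20% target is worded as a difference between two experimental days, a within-person contrast in which stable body size would cancel. Both are fair. The gain matters to the extent that the between-person SD is larger than 6.25.

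**Why fat-free mass?** No section states that secretion depends on it, and the Background points to visceral fat and sex in relation to hepatic fatty-acid delivery. The reference list does cite a study of body composition and VLDL-TG kinetics, which makes the link plausible. Its strength remains an assumption.

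**Conclusion.** The point holds as a modest, inexpensive improvement. For VLDL-TG secretion the plan states neither the endpoint's scale nor any adjustment, and it leaves unused a baseline measurement that it already collects. The benefit is precision, plus protection against a systematic difference in body size or sex mix between non-randomised groups, which could inflate or mask a NAFLD effect.

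Its size depends on the assumed correlation with fat-free mass. At an effect otherwise detectable with power 0.80, adjusted power is about 0.81 to 0.92 for correlations of 0.3 to 0.6 and about 0.77 for none, with break-even near 0.24. The µmol/min shifts in step 5 depend further on assumed proportionality and assumed group differences.

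The documents do not support a claim that the planned test has an inflated error rate, or that this omission leaves the trial underpowered.

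**What to change.** In Statistical analysis, state the scale of VLDL-TG secretion (µmol/min) and prespecify that the groups are compared by ANCOVA with visit-1 DXA fat-free mass as the single covariate, with the unadjusted comparison reported beside it. Apply the same to VLDL-TG oxidation only if it is reported as an absolute whole-body rate.

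A covariate is preferable to dividing by fat-free mass because it does not impose proportional scaling. Keep to one covariate with 20 participants; fat-free mass should also carry much of the sex difference in body size. Report the sex mix and fat-free mass of each group so that readers can judge their overlap.

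The cost is a sentence or two of analysis text, one degree of freedom (17 instead of 18), and about 3 points of power if fat-free mass proves unrelated to secretion. No visit, sample or participant is added.
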